ignored other prevalent tumor types; 2) few studies have examined dose-response effects of specific chemotherapy treatments on cognitive impairment; 3) neuropsychological tests used to characterize chemotherapy-related cognitive impairment provide limited resolution for understanding impairments of specific neural mechanisms; 4) neural factors associated with cognitive impairment have not been sufficiently distinguished from non-neural (e.g. psychosocial) factors. Despite these limitations of current research, chemotherapy-related cognitive impairment affects everyday function and quality of life in cancer survivors. This is a problem that merits further investigation and cannot be ignored.

To overcome these critical limitations of current research on chemotherapy-related cognitive impairment, we propose a two-year pilot study that aims to systematically examine the influence of cancer stage and treatment toxicity on attention abilities in patients diagnosed with a hematological malignancy (HM). We will establish and measure a core battery of behavioral and electrophysiological measures of attention to assess the impact of chemotherapy on this central cognitive ability.

Our specific aims are to:

SA1. Quantify chemotherapy-related attention impairments in HM patients

- H1a. HM groups will not differ from comparison subjects in attention abilities prior to chemotherapy and will perform worse than comparison subjects without cancer or chemotherapy after treatment.
- H1b. Degree of chemotherapy exposure will predict magnitude of attention impairments.
- SA2. Quantify the link between chemotherapy-related attention impairments and electrophysiological measures of attention in HM patients and comparison subjects
 - H2a. HM groups will not differ from comparison subjects in electrophysiological measures of attention prior to treatment but will differ from comparison subjects without cancer or chemotherapy after treatment.
 - H2b. Degree of chemotherapy exposure will predict magnitude of changes in electrophysiological measures of attention.
 - H2c. Electrophysiological measures of attention decline will be predicted by concurrent impairments in behavioral measures of attention (as in H1b).
- SA3. Quantify the effects of chemotherapy-related attention impairment on complex real-world behavior measured in controlled-simulations of on-road driving scenarios designed to challenge driver attention abilities

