Finally, previous studies have used measures with high experimental control and low external validity, providing limited insight into how chemotherapy-related cognitive impairment translates to real-world behavior. It is essential to understand how chemotherapy affects real-world behaviors that could have a profound impact on public health, as impairments in these activities could lead to incursions with the general population. Importantly, identifying which aspects of real-world behaviors are affected by chemotherapy could lead to the development of targeted rehabilitation strategies, ultimately leading to improved cognitive health and quality of life. Thus, combining basic and translational research into future studies will provide better insights into how the lives of chemotherapy patients – and the lives of those in their surroundings – are affected on a daily basis.

Section 3.0 Eligibility Criteria:

Inclusion criteria for HM patients include: 1) HM diagnosis, 2) scheduled to receive treatment based on risk classification, 3) between 19 to 80 years of age, and 4) normal or corrected-to-normal vision. Inclusion criteria for healthy controls will be that they are matched to patient demographics.

Exclusion criteria for HM patients include the presence of: 1) second cancer diagnosis in addition to recent HM diagnosis (however, patients with localized skin cancer may not be excluded), 2) prior radiation or chemotherapy treatment, 3) cognitive impairment (MMSE score <25) prior to baseline assessment, 4) patients who are critically ill or require urgent initiation of chemotherapy will be excluded from this study, 5) patients with any other condition that may not allow safe participation in the study based on the clinical judgment of the treating oncologist will be excluded. Exclusion criteria for healthy controls include HM cancer diagnosis in addition to all exclusion criteria for HM patients. There is the potential to detect cognitive impairment in research participants during cognitive assessment. After

Section 4.0 Registration Procedure:

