Patients will be recruited through the Department of Internal Medicine, Division of Hematology-Oncology with the assistance of Drs. [name], [name], [name], [name], [name], [name], [name], [name], [name], and [name]. Recently diagnosed HM patients will contact – or be contacted by – new patient coordinators to schedule a clinical visit at UNMC. During initial scheduling with new patient coordinators, patient contact information will be recorded in a Patient Tracker, and they will be informed that research is being conducted to study cognitive abilities in HM patients. A brief description of the study will be included in their new patient packet. At the time of their clinical visit, Drs. [name], [name], [name], [name], [name], [name], [name], [name], [name], and [name] will provide further information about the study, and ask patients if they are interested in participating. Interested patients will be screened for inclusion/exclusion criteria, provided with informed consent during their clinical visit, and their demographic information will be collected after consenting to participating in the study. After their clinical visit, a member of the Mind & Brain Health Laboratory (MBHL) will contact consented patients to schedule their initial pre- treatment research study visit. MBHL lab personnel will coordinate with patient case managers to determine their next treatment date so that subsequent study visits can be scheduled accordingly.

Demographically matched healthy controls will be recruited from the MBHL registry and RedCap (#564-10-EP: Building UNMC-based research programs focused on wellness, frailty, and aging) registry based on demographic information collected from HM patients who have already been inducted into the study. Specifically, healthy controls will be matched to HM patients along the dimensions of age (\pm 5 years), gender (same gender), race (same race), and education (\pm 2 years). These registries provide query options for search for specific demographic factors, and are comprised of individuals who have expressed interest in participating in research studies. In addition, spouses or caregivers of chemotherapy patients may be recruited as healthy controls to examine the psychosocial effects of caring for chemotherapy patients on cognitive abilities.

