Given the limited availability for enrollment of HM patients into this study, potential research patients will not be selected based on demographic factors of gender and race. Nevertheless, equal preference will be given to individuals across all gender and race categories.

Research participants that have been recruited into the study will be undergo study induction either in the Division of Hematology/Oncology (HM patients) or in the Mind and Brain Health Labs (healthy controls). After study induction, all research participants will undergo the same testing battery within the Department of Neurological Sciences at each study visit. HM patients will complete each testing battery prior to undergoing their chemotherapy treatment scheduled on the same day.

Research participants will receive monetary compensation (\$20/hour) for their participation. In the event that adequate funding is not secured for compensation, research participants will be recruited as volunteers.

Section 5.0 Treatment Plan of Research Design:

Experimental Design

Patients will be recruited from one of two targeted treatment groups, based on their risk stratification: 1) high risk group for examining the influence of chemotherapy on cognitive impairment; and 2) low risk supportive care treatment schedules, which represents the chemotherapy control group. Additionally, we will recruit a demographically matched (matched at age, gender, and educational status) healthy control group, which will serve as the cancer and chemotherapy control group.

Participants will complete a three-month longitudinal study that will examine the parametric effects of HM-specific chemotherapy treatments on cognitive and electrophysiological measures of attention

mechanisms. We will sample during intervals corresponding to the onset of treatment cycles, thus giving us the opportunity to examine additive dose-response effects of chemotherapy treatment. Sampling intervals for chemotherapy patients (or control patients) will occur according to the following schedule: 1) after HM diagnosis but prior to receiving chemotherapy treatment, providing a baseline assessment, 2) one month after baseline assessment or after one treatment cycle (whichever comes first), 3) three months after baseline assessment after three treatment cycles (whichever comes first).

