There is the potential to detect cognitive impairment in research participants during cognitive assessment. After consent, if a participant receives an MMSE score of 20 or less, they will be discontinued from the study. If cognitive impairment is identified, research personnel will proceed in the following way. First, the participant will be informed that an unexpected finding was encountered that may have clinical significance, and that the clinical significance is best determined in conjunction with his or her primary care physician. Next, research personnel will ask the participant for their permission to contact their primary care physician to help facilitate follow-up to determine clinical significance. The primary care physician will then be contacted and provided clinical context and concerns sufficient to allow for subsequent evaluation, workup, and treatment of any unexpected finding. If the participant refuses to have the research personnel directly contact their physician, the research personnel will offer the participant a written explanation that an abnormal neurological finding was encountered and the written material will include encouragement to have an evaluation, as well as a phone number of the Mind and Brain Health Labs to contact with questions or in case they change their mind.

Section 10.0 Statistical Considerations:

Our primary goal is to examine the effects of chemotherapy on behavioral and electrophysiological measures of cognitive ability in an understudied cancer population. To this end, analyses for the proposed pilot project will be performed on three groups: healthy controls (no cancer, no chemotherapy), very-low to intermediate risk HM patients receiving supportive care treatment (no chemotherapy), and intermediate to very-high risk HM patients receiving chemotherapy treatment.

Statistical Power. Although many of the statistical analyses will involve complex modeling procedures, the main emphasis of our aims and hypotheses is to determine differences between groups and pre-post treatment. Hence, the issue of statistical power can be addressed via consideration of the magnitude of standardized effect sizes that can be detected with reasonable probability. The current study aims to collect pilot data and demonstrate protocol feasibility for future studies and funding opportunities. As such, we plan to obtain 15 samples per group for a total sample size of 45.

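### Spouses and caregivers may be recruited as healthy controls with no label and no planned analysis, which could bias the HM-versus-healthy contrasts towards no difference

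*Combined protocol and SAP*

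**What the plan says.** Section 4.0 (Registration Procedure) recruits matched healthy controls from two research registries. It then adds that "spouses or caregivers of chemotherapy patients may be recruited as healthy controls to examine the psychosocial effects of caring for chemotherapy patients" on cognition. Matching is on age, "gender (same gender), race (same race), and education".

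Section 3.0 (Eligibility Criteria) says only this on inclusion: "Inclusion criteria for healthy controls will be that they are matched to patient demographics". Its exclusions for controls do not mention caregiving.

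Section 5.0 (Experimental Design) describes a matched "healthy control group, which will serve as the cancer and chemotherapy control group". Section 10.0 says that "analyses for the proposed pilot project will be performed on three groups: healthy controls (no cancer, no chemotherapy"), followed by two HM patient groups, with 15 participants planned per group. The models listed there use treatment group and task factors. None has a caregiver term.

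The hypotheses in Section 1.0 rest on this reference group. H1a, for example, begins: "HM groups will not differ from comparison subjects in attention abilities prior to chemotherapy". It then predicts worse performance in patients after treatment.

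**The concern.** A reference group should be free of exposures thought capable of changing the outcome. Here the reason given for admitting caregivers is to study whether caring for a patient affects cognition, and cognition is what the study measures. Nothing in the plan caps their number, labels them, models them or repeats the analysis without them.

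Two things are at stake. First, if caregiving lowers attention, the control mean moves towards the patients, and a real deficit in patients looks smaller. Section 10.0 says that the pilot is meant to estimate effect sizes for later, fully powered studies, so the bias would be carried into their design. Second, the caregiver question itself cannot be answered as planned, because no analysis separates caregivers from registry controls.

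This also cuts across the plan's own rationale. Section 1.0 criticises earlier research for failing to separate neural from psychosocial causes.

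**Working it through.** **The plan's own figure.** The pilot's 15 per group has no power basis to reproduce. Section 10.0 does give one for future studies: 32 per group, 80% power, two-sided alpha 0.01, and effects of 0.65 SD within group and 0.9 SD between groups. With the noncentral t distribution, power at 32 is 81.7% within and 82.3% between, and the minimum detectable effects are 0.64 and 0.88. The figure reproduces, so the point does not rest on an arithmetic error in the plan.

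**Inputs for the bias.** There are 15 controls (Section 10.0), and the healthy-control response-time SD is 213.23 (Section 10.0). The number of caregivers k and their deficit g are not in the documents. Assumed: k = 3, 5 or 8, and g = 0.3 or 0.5 SD.

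**Shift in the control mean** = k × g / 15:

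| k | g = 0.3 SD | g = 0.5 SD |
|---|---|---|
| 3 | 0.06 | 0.10 |
| 5 | 0.10 | 0.17 |
| 8 | 0.16 | 0.27 |

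In response-time units the range is 0.06 × 213.23 ≈ 13 to (4/15) × 213.23 ≈ 57.

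**Comparison with the pilot's precision.** The standard error of a difference between two groups of 15 is √(1/15 + 1/15) = √(2/15) ≈ 0.37 SD. Every value in the table is below one standard error. Unlike sampling error, though, the shift does not shrink as the sample grows. At 32 per group the standard error is √(2/32) = 0.25 SD, and with the same share of caregivers the largest assumed shift (0.27 SD) would slightly exceed it.

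**Effect on a later study.** Suppose the true difference is 0.9 SD, a share f of controls are caregivers, and alpha is 0.01 two-sided. The expected difference becomes 0.9 − f × g, and the control variance becomes 1 + f(1 − f)g². Power by noncentral t:

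| f | g (SD) | Power, 32 per group | Power, 15 per group |
|---|---|---|---|
| 0 | – | 82% | 40% |
| 1/5 | 0.3 | 75% | 34% |
| 1/3 | 0.3 | 70% | 30% |
| 1/3 | 0.5 | 60% | 24% |
| 1/2 | 0.5 | 47% | 18% |

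If the diluted pilot estimate were instead used to size a later study, the normal-approximation sample size for 80% power would rise from 29 per group to 37 (f = 1/3, g = 0.3) or 45 (f = 1/3, g = 0.5).

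**Which contrasts are touched.** The shift applies to patient-versus-healthy comparisons at a given visit, which is how H1a, H2a and H3a are worded. At baseline, a caregiver deficit could hide a real pre-treatment deficit in patients, and H1a predicts that there is none. A deficit that stays constant over the three visits cancels from a comparison of changes from baseline. Chemotherapy versus supportive care involves no healthy controls and is untouched.

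**The case against.** The case on the other side has several sound parts.

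- **The plan does not predict a caregiver effect.** A reader might infer that the sponsor expects caregiving to impair cognition. The wording is optional and poses a question, and the predictions in Section 10.0 include none about caregivers. This objection stands.
- **Pooling is not stated outright.** The sentence opens as an addition to registry recruitment, so caregivers might supplement the 15. Recruiting them as healthy controls into a three-group analysis points the other way, but the documents do not settle it. This stands as a limit on certainty.
- **Some mitigation exists.** Section 5.0 (Experimental Control Measures) collects a depression inventory and health, medication and life-space questionnaires from patients and controls. These enter the model if linked to performance. That helps, but inclusion is conditional, the factors are framed as ones affected by HM disease and treatment, and caregiver status and burden are not listed.
- **A comparison group for caregivers exists.** Registry controls could serve. What is missing is a planned analysis.
- **The same-gender rule shows no defect.** A reader might infer that spouses break the matching. An opposite-gender spouse cannot match his or her own partner but can match another patient, and not every caregiver is a spouse.
- **Caregiver controls might be useful.** Controls who share the psychosocial burden could help isolate the effect of treatment. That is true only if they can be identified in the data.

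**Conclusion.** The point holds as a design weakness of unknown size. A written recruitment rule can place a possible cause of the outcome, unlabelled, in the only healthy reference group, and the question that motivates the rule has no planned analysis. The bias is towards no difference if caregiving lowers attention. Under the assumed 3 to 8 caregivers among 15 controls and the assumed 0.3 to 0.5 SD deficit, it is 0.06 to 0.27 SD, less than the pilot's standard error of about 0.37 SD. It matters mainly because the pilot's estimates are meant to inform later studies.

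Three stronger readings are not supported. The documents do not show that the control group is contaminated, since no caregiver need be enrolled. The 0.9 SD effect is not this pilot's planned difference: Section 10.0 gives it as what a future study with 32 per group could detect. And nothing in the documents shows that a caregiver effect would grow over the three months, so bias in change from baseline is a possibility only.

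**What to change.** Amend Sections 4.0 and 10.0 to:

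1. record caregiver or spouse status for every control;
2. state that caregivers and spouses do not count towards the 15 matched controls in the main HM-versus-healthy contrasts;
3. analyse any who are enrolled as a labelled descriptive group against the registry controls.

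If the sponsor prefers to keep them in the control group, add a caregiver indicator to the models and a sensitivity analysis without them.

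The cost is a few sentences and one data field. The downside is that all 15 main controls must come from the two registries already named in Section 4.0, both of which can be searched on demographic factors. Caregiver status should be recorded from the first control enrolled, since the separation may not be recoverable later.

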Capture task. Capture tasks⁷⁰⁻⁷⁴ are an ideal candidate for studying attention because they offer experimenters a tool to precisely measure the *cost of processing an irrelevant stimulus* within a capturing display (*inhibitory control* mechanism) and the *timecourse of releasing attention* when it is captured by an irrelevant stimulus (*disengagement speed* mechanism).

In this task (Figure 2), participants are instructed to identify a target item (e.g. a green square with a notch on one side) presented among multiple distractor items within a search display; prior to the search display, a brief capture display is presented that contains a colored distractor item similar (contingent condition) or dissimilar (singleton condition) to the target color. Performance is measured as response time to correctly identify and respond with the location of the notch in target items. Previous studies have demonstrated: 1) longer reaction times in the contingent condition relative to the singleton condition, because attention is more likely to be distracted by a contingent stimulus that matches the target stimulus color, and 2) shorter reaction times in both conditions at longer inter-stimulus intervals (ISI; time difference between capture display and search display), because attention is more likely to disengage from the capturing stimulus prior to the onset of the search display when ISIs are longer.

In the current proposal, we will be able to directly measure the effects of chemotherapy treatment on inhibitory control mechanisms as they apply to the suppression of an irrelevant stimulus and disengagement mechanisms as they apply to the release of captured attention from an irrelevant stimulus.

Figure 2: Capture Task Schematic

Filtering task. Filtering tasks^{75,76} are an ideal candidate for studying attention because they offer experimenters a tool to precisely measure the *amount of information* that can be simultaneously attended (*storage capacity* mechanism) and the efficiency to *filter out irrelevant information* embedded among relevant information (*inhibitory control* mechanism).

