Contralateral Delay Activity (CDA). The CDA component has been used in multiple empirical studies to examine neural mechanisms of attention specific to storage capacity because it tracks both which information is being stored in mind and how much information is being stored in mind ^{75,76,84}. The CDA component is a sustained relative negative amplitude modulation in posterior electrodes that onsets at approximately 300-400 milliseconds, with more negative amplitudes occurring in electrodes contralateral to the remembered visual field (Figure 4 right panel). CDA *amplitude* tracks online storage, where larger amplitudes suggest that more items are stored in mind^{75,76}. Here, the CDA will be used to measure chemotherapy-related differences in storage capacity during the filtering task.

Figure 4: Electrophysiological Components: N2pc (Left), Pd (Middle), CDA (Right)

Driving Simulation

The goal of Specific Aim 3 is to implement simulations of driving scenarios that integrate laboratory-based attention mechanisms into a naturalistic environment that requires the coordination of multiple cognitive domains, including attention. By selectively challenging distinct attention mechanisms under different driving conditions and loads (e.g. traffic, pedestrians, road signs), we will be able to evaluate how impairments in attention affects driving outcomes. Broadly speaking, the goal of testing patients in simulated driving scenarios is to determine how computer-based cognitive tasks (SA1) translate into real-world driving behavior.

Car following task. The car following task requires drivers to follow a lead vehicle at a constant distance of two car lengths^{85,86}. During this task, the lead vehicle pseudo-randomly changes its velocity, requiring drivers to vigilantly attend the lead vehicle to avoid an incursion while maintaining the instructed two-car length distance. Critically, the lead vehicle will occasionally brake during the drive, requiring drivers to rapidly brake in order to avoid collision. If attention is not fixed on the lead vehicle, an accident will likely occur. Outcome measures for the car following task include: 1) *mean distance* between lead vehicle and driver, 2) *brake delay*, measured as the delay between lead vehicle and driver braking time, and 3) *crash*, a binary variable that indicates if a collision occurred.

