□ Response time (Capture Task) and response accuracy (Filtering Task) Electrophysiology

□ Amplitude and latency of N2pc, Pd, and CDA electrophysiological components Driving Simulation

- Response time (Visual Search Task)
- Brake time, mean following distance, and number of incursions (Car Following Task)
 CRP
 - Concentration levels of circulating inflammatory proteins

OCT

Surface area and volume of retinal ganglion cell layer and optic nerve fiber

Given that we are not proposing an intervention trial our primary outcome measures will not be related to the progression of HM.

Section 7.0 Study Parameters:

Summary of Study Events and Durations. Each study visit is anticipated to take approximately 2.5 hours to complete. Table 1 contains a summary for the schedule of study events to occur at each research component. Study induction takes place at the beginning of Visit 1. Time requirements for research participants at each study event are as follows:

- □ Study Induction (~.5 total hours):
 - Informed consent (20 minutes)
 - Demographic Information (10 minutes)
 - Comorbidity Index (conducted offline)
 - Anemia Evaluation (conducted offline
- □ Each Study Visit (~2.5 total hours):
 - Cognitive Battery (40 minutes)
 - Electrophysiology (15 minutes)
 - Driving Simulation (20 minutes)
 - Neuropsychological Exams (45 minutes)
 - Health & Mobility Questionnaires (10 minutes)
 - OCT (10 minutes)
 - Blood Collection (10 minutes)

	Pre- Induction	Study Induction	Visit 1 (Month 0)	Visit 2 (After Month 1 or 1 treatment	Visit 3 (After Month 3 or 3 treatment
				cycle)	cycles)
HM Diagnosis	X				
Control Group ID	X				
Informed Consent		Х			
Demographic Information		Х			
Comorbidity Index		Х			
Anemia Evaluation		Х			
Chemotherapy Treatment			X	X	X
Cognitive Battery			X	Х	Х
Electrophysiology			X	Х	X
Driving Simulation			X	Х	Х
Neuropsychological Exams			X	X	X
Health & Mobility Questionnaires			X	X	X

OCT		Х	Х	X
Blood Collection/ Protein Assay		Х	X	X

Section 8.0 Drug Formulation and Procurement:

This pilot study is not a pharmaceutical trial.

Section 9.0 Toxicity and Adverse Event Reporting Guidelines:

This research has been classified as Minimal Risk.

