While we realize we will not have sufficient power to declare smaller effects statistically significant, as this is a pilot study, it will allow us to estimate effect sizes for a number of outcomes to conduct fully powered studies. In future large-scale confirmatory studies, with a sample size of 32 per group, we will have 80% power to detect a standardized effect size of 0.65 (a medium to large effect) for within group changes, and an effect size of .9 for between group differences. These power calculations assume a two-tailed alpha of 0.01 to informally adjust for multiple comparisons and multiple testing. A standardized effect size of 0.65 corresponds to a 10% difference in response time from healthy controls (mean=1394.75, standard deviation = 213.23). This sample size will allow adequate power to detect medium to large effects within group, and large effects between groups.

Statistical Analysis. To assess the data collected, for each group, we will first produce frequency tables, calculate descriptive statistics, and create univariate graphs (e.g. box-plots, histograms) on the

predictor and response variables to investigate distributional properties and check for outliers in the data. Although the specific statistical models that we will use to test our formal hypotheses and to calculate confidence intervals will depend on the outcome distributions that we observe in our data, we anticipate using linear mixed models and generalized linear mixed models, as appropriate. This modeling approach allows us to properly account for the distribution of the outcome measure while also properly modeling repeated effects and adjusting for potentially confounding variables. Confidence intervals of all effects will be calculated in order to assess clinical significance of statistical results.

We will employ linear mixed models and general linear models to **assess** within-subject, betweensubject, and mixed effects of:

- Behavior:
 - Capture condition, stimulus ISI, and treatment group on response time measures in the Capture Task
 - Filtering condition, storage load, and treatment group on response accuracy measures in the Filtering Task
- Driving simulation:
 - Treatment group on response time measures in the Visual Search Task
 - Treatment group on lead car distance variability, brake time, and number of incursions during the Car Following Task
- □ Electrophysiology:

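### Response time in the Capture and driving Visual Search Tasks has no error rate beside it, and brake delay has no rule for events without braking, so these contrasts cannot be read on their own

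*Combined protocol and SAP*

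**What the plan says.** **Capture Task.** Section 5.0 (Attention Battery) states: "Performance is measured as response time to correctly identify and respond with the location of the notch in target items". Section 6.0 lists "Response time (Capture Task) and response accuracy (Filtering Task"), so accuracy is planned for Filtering but not for Capture. The Section 10.0 model is for "Capture condition, stimulus ISI, and treatment group on response time measures in the Capture Task".

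**Driving Visual Search Task.** Section 6.0 lists "Response time (Visual Search Task") and Section 10.0 models "Treatment group on response time measures in the Visual Search Task". Neither names an error outcome, and neither says whether incorrect responses are left out.

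**Car Following Task.** Section 5.0 (Driving Simulation) defines brake delay as "measured as the delay between lead vehicle and driver braking time" and crash as "a binary variable that indicates if a collision occurred". Section 6.0 lists brake time and number of incursions, and Section 10.0 models both by treatment group. No rule covers a lead-car braking event in which the driver does not brake.

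**The concern.** Response time reflects both how efficiently a person processes the display and how cautious they choose to be. Without errors, the two cannot be separated. Section 10.0 distinguishes its three Capture hypotheses partly by whether response times rise in both conditions and whether the contingent-minus-singleton difference rises. A shift in caution with illness, fatigue or repeated testing could change that pattern with no matching change in attention.

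Brake delay has a different problem. The events with no value are the worst ones, and they should be commoner in a group with poorer attention. The plan itself says: "If attention is not fixed on the lead vehicle, an accident will likely occur".

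Specific Aims 1 and 3 rest on these contrasts, and the pilot is meant to supply effect sizes for later powered studies. A distorted effect size would carry forward.

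**Working it through.** **1. The plan's own figure.** Section 10.0 equates a standardised effect of 0.65 with a 10% response-time difference (mean 1394.75, SD 213.23). Check: 0.10 × 1394.75 = 139.475, and 139.475 / 213.23 = 0.654. This agrees, so the target is stated in response time alone. If lower caution hid 25%, 50% or 75% of that slowing (my assumption), the observed effect would be 0.49, 0.33 or 0.16.

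**2. Response time with a shift in caution.** The documents give no error rates, so every value here is assumed. I use a two-choice diffusion model with noise s = 0.1 and non-decision time 0.73 s. Drift v stands for processing efficiency and threshold a for caution.

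- P(correct) = 1 / (1 + exp(−va/s²))
- Mean response time = 0.73 + (a/2v) × tanh(va/2s²)

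| Case | v | a | va/s² | Errors | Mean response time |
|---|---|---|---|---|---|
| Reference | 0.15 | 0.20 | 3.000 | 4.7% | 0.73 + 0.667 × 0.905 = 1.333 s |
| 20% less efficient, less cautious | 0.12 | 0.182 | 2.184 | 10.1% | 0.73 + 0.758 × 0.798 = 1.335 s |
| 20% less efficient, same caution | 0.12 | 0.20 | 2.400 | 8.3% | 0.73 + 0.833 × 0.834 = 1.425 s |
| Same efficiency, more cautious | 0.15 | 0.22 | 3.300 | 3.6% | 0.73 + 0.733 × 0.929 = 1.411 s |

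Row 2 hides a real deficit: response time is unchanged within 2 ms while errors double. Row 4 mimics one: response time is 78 ms longer with no loss of efficiency. Row 3 shows the deficit as about 91 ms. Errors separate these cases and response time alone does not.

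**3. Brake delay, selected on having braked.** Assumed values: controls mean 1.2 s, SD 0.3; patients mean 1.5 s, SD 0.4; no value beyond a collision at time c. With b = (c − m)/s and λ = φ(b)/Φ(b), the observed mean is m − sλ and the observed SD is s√(1 − bλ − λ²).

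At c = 2.0 s:
- Controls: b = 2.667, λ = 0.0114, mean 1.197, SD 0.295, 0.4% of events lost.
- Patients: b = 1.25, λ = 0.2042, mean 1.418, SD 0.335, 10.6% of events lost.
- Difference: 1.418 − 1.197 = 0.22 s instead of 0.30 s, 26% smaller.
- Standardised effect: 0.2217 / √((0.295² + 0.335²)/2) = 0.70, against 0.30 / √((0.3² + 0.4²)/2) = 0.85, about 17% smaller.

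The result depends on the cut-off:

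| Collision time | Control mean | Patient mean | Observed difference |
|---|---|---|---|
| 1.8 s | 1.183 | 1.344 | 0.16 s |
| 2.0 s | 1.197 | 1.418 | 0.22 s |
| 2.5 s | 1.200 | 1.493 | 0.29 s |

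**The case against.** Much of the case against a stronger reading stands.

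- **Drivers who never brake.** A reader might infer that they look unimpaired. The documents do not support this. Crash is defined in Section 5.0 and incursions are modelled in Section 10.0, which also predicts more crashes with longer brake delays. In the example above, the loss of 0.4% against 10.6% of events would itself show in the incursion count. What remains is that brake delay is a separate contrast and does not include those events.
- **Dropping error trials.** A reader might infer that limiting Capture to correct responses itself pushes the contrast towards no effect. In the model used here, correct and error response times have the same distribution, so the restriction leaves the mean unchanged. The masking in row 2 comes from the assumed drop in threshold, and row 4 shows bias the other way.
- **Visual Search.** A correct-only rule might be inferred, but none is stated. The gap there is only the missing error outcome.
- **Other measures.** N2pc and Pd are analysed in both tasks, the Filtering Task measures accuracy, and UFOV, PASAT and Stroop are administered. A deficit would not necessarily go unseen across the study. These measures do not make the Capture or Visual Search response-time contrasts interpretable.
- **Scope of the illustration.** It concerns overall mean response time. The planned inhibition measure is the contingent-minus-singleton difference, whose bias is not sized here.
- **Pilot status.** With 15 per group and models left to depend on observed distributions, this is a modest point. It still matters, because effect sizes are what the pilot is meant to deliver.

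**Conclusion.** The concern holds in a limited form. Capture performance is response time to a correct response, and no error rate is planned for Capture or Visual Search. A difference in caution between groups or visits can therefore hide or mimic an attention deficit in those contrasts. The documents do not fix the direction or size of this bias, and the diffusion figures show only that both directions are possible.

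For brake delay the likely direction is clearer. Selection on having braked would tend to understate slowing: 0.22 s instead of 0.30 s at a 2.0 s cut-off (0.16 s at 1.8 s, 0.29 s at 2.5 s), or 0.70 instead of 0.85 standardised at 2.0 s. This rests on assumed normal delays, assumed means and SDs, and one fixed collision time. The failed events are not lost to the study, since crash and incursions record them.

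This is a worthwhile and cheap improvement to the outcomes of Specific Aims 1 and 3, not a fatal flaw.

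**What to change.** In Sections 6.0 and 10.0:

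1. Add error rate as an outcome for the Capture and Visual Search Tasks, using a binomial mixed model with the same factors as the matching response-time model.
2. Read errors and response time together. When errors move in the opposite direction, do not interpret a response-time difference as a change in attention, or its absence as preserved attention.
3. Analyse brake delay per lead-car braking event as time-to-event, censored at collision when the driver did not brake. Adjust for following distance at lead-car braking, because collision time depends on it. Report the result beside the incursion count.

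The cost is a few more outcomes to report and some extra analysis. Section 11.0 keeps performance records in raw form, so the data are expected to be available without new testing; confirm that the logs hold response correctness and event-level braking and collision times. Following distance is itself a study outcome, so the adjusted brake-delay contrast compares drivers at equal distance and should be described that way.
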